5.1.2. Data Handling Rules

For analysis purposes the \log_{10} qRT-PCR viral load will be imputed with 2.12 when the result is ‘TARGET DETECTED’ (ie, below limit of quantification: <2.18) and with 2.05 if result is ‘TARGET NOT DETECTED’ (ie, below limit of detection: <2.05). The \log_{10} TCID₅₀ viral titer will be imputed with 0.74 when the result is ‘<0.75’ (below limit of detection and quantification).

5.1.3. Stratification Factors

The actual values of the stratification factors will be used for all analyses.

The concomitant medications indicated as standard-of-care treatment on the concomitant medication form will be used for determining the actual strata for type of baseline SOC. If no influenza antiviral is recorded it will be assumed that the subject received SOC not including influenza antiviral. The following ATC level 4 code and generic medication names indicate an influenza antiviral:

- J05AH (including neuraminidase inhibitors)
- Laninamivir
- Umifenovir
- Amantadine
- Rimantadine
- Ribavirin
- Baloxavir Marboxil

The datetime when first acute respiratory symptoms appeared and the datetime of first dose of study drug will be used for determining the actual strata for time since symptom onset relative to

treatment initiation. There will be no missing stratification factor values for randomized subjects receiving study drug.

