## 3. STUDY DESIGN AND RATIONALE

### 3.1. Overview of Study Design

This is a Phase 3, randomized, double-blind, placebo-controlled, multicenter study to evaluate the efficacy and safety of pimodivir in combination with SOC treatment versus placebo in combination with SOC treatment in adolescent (13 to 17 years), adult (18 to 65 years), and elderly (>65 to ≤85 years) non-hospitalized subjects with influenza A infection who are at risk of developing complications. A target of 720 subjects will be randomly assigned in this study with 360 subjects planned per treatment arm. The aim is to enroll a minimum of 72 adolescent subjects in this study in selected countries and study sites consistent with local regulations. The target population of the study are influenza-infected, non-hospitalized subjects who, due to their age (65 to 85 years) or underlying comorbidities (regardless of age), are at increased risk of developing influenza-related complications. The randomization will be stratified by type of baseline SOC (including or not including antiviral treatment) and time since onset of symptoms (first administration of study drug ≤48 hours or >48 hours since onset of influenza symptoms). The study population should consist of at least 60% of subjects with first administration of study drug ≤48 hours since onset of influenza symptoms .

Subjects who meet all eligibility criteria will be randomized in a 1:1 ratio to receive 1 of the following 2 treatments:

- Treatment Arm 1: pimodivir 600 mg bid for 5 days + SOC treatment\*
- Treatment Arm 2: pimodivir placebo bid for 5 days + SOC treatment\*

\* SOC treatment will be determined by the investigator based on local practice, and may include influenza antivirals and/or supportive care only. The choice to use influenza antivirals as part of the SOC should be made before randomization. The influenza antiviral should be started no later than Day 2 morning (up to noon). An influenza antiviral as part of the SOC cannot be changed (eg, switching one influenza antiviral for another) during the treatment period, with the exception that an influenza antiviral may be discontinued in the case of a suspected AE.

Study drugs will be taken orally. Refer to the pharmacy manual/study site investigational product manual for additional guidance on study drug preparation, handling, and storage.

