## **8. PRESTUDY AND CONCOMITANT THERAPY**

Prestudy therapies administered up to 30 days before first dose of study drug must be recorded at screening.

Concomitant therapies must be recorded throughout the study beginning with start of the first dose of study drug through the Final Study Visit/Safety Follow-up Visit. Medications that are part of the SOC should be recorded as concomitant medications throughout the study. Concomitant therapies should also be recorded beyond Final Study Visit/Safety Follow-up Visit if in conjunction with SAEs that meet the criteria outlined in Section 12.3.2. Serious Adverse Events.

To avoid the confounding effects of antipyretic medications, temperature measurements must be taken, whenever possible, at least 4 hours after administration of the antipyretic medication.

All therapies (prescription or over-the-counter medications, including vaccines, vitamins, herbal supplements; non-pharmacologic therapies such as electrical stimulation, acupuncture, special diets, exercise regimens) different from the study drug must be recorded in the eCRF. Recorded information will include a description of the type of the drug, treatment period, dosing regimen, route of administration, and its indication.

The following pre-study and concomitant therapies are disallowed:

1. More than 1 dose of influenza antiviral medication (eg, OST, zanamivir), or ribavirin within 2 weeks, prior to first study drug intake.
2. IV peramivir more than 1 day prior to screening.
3. An investigational drug (including investigational vaccines) or an invasive investigational medical device within 30 days, or an investigational biological product within 3 months or 5 half-lives (whichever is longer) prior to the first dose of study drug until the end of the study.
4. Use of a live attenuated intranasal spray influenza vaccine within 3 weeks before study entry.

Substrates of OATP1B1 and/or OATP1B3, including atrasentan, bosentan, ezetimibe, glyburide, irinotecan, repaglinide, rifampin, telmisartan, valsartan, and olmesartan may be continued. Statins (ie, 3-hydroxy-3-methylglutaryl-coenzyme A [HMG CoA] reductase inhibitors) may also be continued, but subjects should be cautioned and observed for potential statin-related toxicity.

The sponsor must be notified in advance (or as soon as possible thereafter) of any instances in which prohibited therapies are administered.

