### ***Primary Endpoint***

Time to resolution of the 7 primary influenza-related symptoms is defined as the time from initiation of study treatment to when all symptoms are considered resolved for at least 24 hours. A symptom is considered resolved, depending on pre-existence of the symptom:

- The symptom is pre-existing:
  - The symptom is considered resolved if post-baseline severity is equal or lower than the pre-existing severity
- The symptom is not pre-existing:
  - The symptom is considered resolved if its severity is scored at most mild post-baseline

The primary efficacy analysis of the time to resolution of the 7 primary influenza-related symptoms (cough, sore throat, headache, nasal congestion, feeling feverish, body aches and pains, fatigue) will consist of a stratified Gehan-Wilcoxon test (using the randomization stratification factors, ie, type of baseline SOC and time since onset of symptoms as strata). Kaplan-Meier curves, overall and by stratum, and a stratified log-rank test for time to symptom resolution will also be provided. Additionally, the data will be analyzed using an accelerated failure time model. Also, a Cox proportional hazards model will be applied. Both models will be adjusted for stratification factors and baseline symptom domain score.

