2.2.2. Efficacy Analysis Sets

Efficacy will be analyzed on the intent-to-treat infected (ITT-i) set and by randomized treatment. The primary efficacy endpoint will also be analyzed on the Per Protocol set. The primary efficacy endpoint and the two most important secondary endpoints (ie, 'Incidence of treatment-emergent adjudicated influenza complications' and 'Incidence of hospital admission 28 days after treatment initiation') will also be analyzed on the intent-to-treat non-infected (ITT-ni) set and by randomized treatment.

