2.2.2.2. Per Protocol Set (PP)

All subjects in the ITT-i set without major protocol deviations that may have an impact on the efficacy analysis.

Decisions regarding which subjects are included in the per protocol set will be made before database lock on the following criteria. Subjects will be included in the PP set in case:

- Subjects missed at most 3 doses in total or at most 2 consecutive doses. On the day of randomization or the next day at least one dose needs to be taken.
- The actual treatment must be the same as the planned treatment
- No unblinding may have taken place
- Subjects may not violate inclusion criteria 2, 3, 5, and 12 and exclusion criteria 1, 6, 9, 12, and 13. For details of these in/exclusion criteria refer to [Table 5](#).
- Screening PRO assessments (Pre-existing Symptom Questionnaire and Flu-iiQ™ Module 1) performed on the ePRO device before randomization.
- Completed the pre-existing symptoms questionnaire and have at least 3 post-baseline Flu-iiQ™ measurements.
- Influenza antiviral as part of the SOC was started no later than Day 2 morning.
- Subjects did not switch to another influenza antiviral as a part of the SOC during the treatment period.

Table 5: Details of inclusion and exclusion criteria to be fulfilled for inclusion in the per protocol analysis set

Inclusion/Exclusion	Criterion number	Description
Inclusion	2	Present to the clinic with symptoms suggestive of a diagnosis of acute influenza and have at least 1 respiratory symptom and at least 1 systemic symptom, both scored as at least 'moderate' if the symptom did not pre-exist before influenza onset, or scored worse than usual if the symptom pre-existed as determined by subject's ratings on Module 1 of the Flu-iiQ™ and the Pre-existing Symptom Questionnaire in the ePRO device. Symptoms must include the following by category: 
 1. Respiratory symptoms: cough, sore throat, nasal congestion, 2. Systemic symptoms: headache, body aches or pain, feverishness, fatigue.
Inclusion	3	Tested positive for influenza A infection after the onset of symptoms, using a rapid influenza diagnostic test (RIDT) or, if available, a PCR-based or other rapid molecular diagnostic assay.
Inclusion	5	Enrollment and initiation of study drug treatment ≤ 72 hours after onset of influenza symptoms.

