2.3. Definition of Subgroups

See [Table 6](#) for the definitions of all the subgroups. The third column in the table indicates for which endpoints the subgroup is applied.

Descriptive statistics will be produced for the different subgroups.

In demographics and baseline disease characteristics, the following subgroups will be used:

- Region
- Influenza A subtype category
- Age group
- Time since onset of influenza symptoms (actual)
- Type of SOC at baseline (actual)
- Influenza season
- Study period
- Baseline resistance
- Any baseline polymorphism
- COVID-19 impacted

Stratification factors (actual) will be used as subgroups for concomitant medication.

For the primary and two most important secondary endpoints (ie, 'Incidence of treatment-emergent adjudicated influenza complications' and 'Incidence of hospital admission 28 days after treatment initiation') the subgroup with subgroup*treatment interaction term will be added in the statistical analysis models, except for the study period subgroup, where the analysis will be performed separately for each individual category of the subgroup. For further details see Section 5.2.3 and Section 5.3.2. For other endpoints, the statistical analysis will be performed separately for each individual category of the subgroup.

Table 6: Subgroups with their definition

Subgroup	Definition	Endpoints
Region	Based on country according to UN classification of Geographic regions ^[5] : 
 • Europe/Africa • Northern-America • Latin America and the Caribbean • Asia and Oceania 	- Efficacy (primary and secondary endpoints, excluding viral kinetics endpoints)
Age group (years)	
 • 13-17 years • 18-65 years • 66-85 years 	- Efficacy (primary and secondary endpoints, excluding viral kinetics endpoints) - All safety
Type of SOC at baseline (actual)	
 • SOC including influenza antiviral treatment • SOC not including influenza antiviral treatment 	- All efficacy - Viral phenotype - Viral genotype - Safety (AE summary, AEs and SAEs by MedDRA system organ class and preferred term, influenza-related complications, laboratory toxicity)
Time (hours) from onset influenza symptoms to	
 • ≤48 hours • >48 hours 	- All efficacy - Viral phenotype - Viral genotype

Subgroup	Definition	Endpoints
first study drug intake (actual)		

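### SAP 5.1.3 sets the actual baseline-SOC stratum from SOC-flagged antivirals with no start-date limit, so a late start could change it: a minor gap that one clause closes

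*SAP*

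**What the plan says.** SAP 5.1.3 is explicit on which values enter the models: "The actual values of the stratification factors will be used for all analyses". For the SOC factor, the drugs flagged as standard of care "on the concomitant medication form will be used for determining the actual strata for type of baseline SOC". A subject counts as having no antiviral only if no influenza antiviral is recorded. The section sets no start date or time.

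The form covers the whole study. Protocol 8 says: "Medications that are part of the SOC should be recorded as concomitant medications throughout the study".

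The conduct rule is separate. Protocol 3.1 says: "The choice to use influenza antivirals as part of the SOC should be made before randomization". The same paragraph, repeated in SAP 1.2, asks for the antiviral to start by noon on Day 2. The SAP carries that limit into two definitions. One Per Protocol criterion (SAP 2.2.2.2) reads "Influenza antiviral as part of the SOC was started no later than Day 2 morning", and SAP 2.6 puts the same limit on the oseltamivir (OST) subset. It does not carry the limit into 5.1.3, the ITT-i definition (2.2.2.1) or the SOC subgroup (2.3).

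The actual factor then enters the stratified Gehan-Wilcoxon test (5.2.3), the logistic models for the two confirmatory secondary endpoints (5.3.2), and the supportive accelerated failure time and Cox models. SAP 4.1 tabulates SOC both as randomized and actual, but no analysis uses the randomized value.

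**The concern.** A factor labelled baseline should not be changeable by what happens after randomization. Read literally, an antiviral started on Day 5 and flagged as SOC makes the subject a baseline-antiviral subject. Such a start may follow persisting symptoms, which is the primary endpoint, or a complication or admission, which are the confirmatory secondary endpoints. The stratum could then depend on outcome. If that dependence differed by arm, the arms would no longer be comparable within strata, and the p-value could be off in either direction. The Per Protocol criterion shows that the authors foresaw late starts, while the ITT-i set keeps those subjects.

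Three things are outside the point. The OST-subset tests drop this factor (SAP 5). The per-arm Kaplan-Meier medians that measure the treatment effect (5.2.2) are unstratified. The onset-time factor is fixed by symptom onset and first dose.

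**Working it through.** **The plan's own figures first.** For a shift on log time with a logistic error, Wilcoxon power is approximately Φ(−ln(0.75) / (scale × √3 × √(2/300)) − 1.96), with 300 per arm and a 25% reduction.
- Scale 0.5213: 0.2877/0.0737 − 1.96 = 1.94, power 97.4% (stated 97.3%).
- Scale 0.5867: 0.2877/0.0830 − 1.96 = 1.51, power 93.4% (stated 93.3%).

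Both Gehan-Wilcoxon figures for the log-logistic model (Protocol Table 3, SAP Table 2) reproduce. The separate statement of 90% at scale 0.55 does not: the formula gives 95.9%. That does not bear on this point.

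**How many subjects could move.** No late-start rate or baseline antiviral share is given, so these are assumptions. Suppose late starts occur among no-antiviral subjects still unresolved at 72 h. Under the sample-size model (log-logistic, intercept 5.0, scale 0.55) the share unresolved at 72 h is 1/(1 + exp((ln 72 − 5.0)/0.55)) = 1/(1 + 0.268) = 0.788. With half the subjects on no antiviral, 0.5 × 0.788 = 39.4% could start late. A late-start rate of 5%, 20% or 30% then moves 2.0%, 7.9% or 11.8% of all subjects.

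**What to expect.** If late-start rates are equal by arm and there is no treatment effect, reclassification depends on outcome but not on arm. The arms stay exchangeable within the actual strata, so error should stay nominal. It can move only if rates differ by arm.

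**Simulation of the primary test.** Inputs from the plan: 600 ITT-i subjects, 1:1, scale 0.55, intercept 5.0, and the inverse-normal combination of SAP 5.1.1. Assumed inputs:
- blocks of 4 and four strata, with 40% starting treatment after 48 h;
- 20, 50 or 80% of subjects without antiviral;
- antiviral either not prognostic or shortening recovery by 20%;
- censoring at 27 days;
- interim at N1 = 450 of 720 (375 and 225 ITT-i by stage), with no sample size increase. The weights are √(450/720) = 0.791 and √(1 − 450/720) = 0.612.

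There were 10,000 null trials per case (Monte Carlo SE 0.0016) and 5,000 per case for power. One-sided error, nominal 0.025:

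| Late starts, placebo:pimodivir | Actual SOC | SOC as randomized |
|---|---|---|
| Equal (5, 20 or 30%) | 0.023–0.028 | 0.024–0.029 |
| Mildly unequal (5:3) | 0.023–0.029 | 0.023–0.027 |
| Large differences (20:10, 30:10, 10:20) | 0.005–0.044 | 0.023–0.027 |

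At equal rates, using actual rather than randomized SOC changes power by −1.4 to +1.2 points. The large-difference cases under actual SOC break down as follows:

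| Without antiviral | Antiviral prognostic | 20:10 | 30:10 | 10:20 |
|---|---|---|---|---|
| 20% | no | 0.028 | 0.033 | 0.022 |
| 20% | yes | 0.030 | 0.039 | 0.018 |
| 50% | no | 0.026 | 0.027 | 0.024 |
| 50% | yes | 0.034 | 0.041 | 0.017 |
| 80% | no | 0.013 | 0.005 | 0.044 |
| 80% | yes | 0.016 | 0.009 | 0.041 |

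The direction is not fixed: more late starts on placebo can make the test liberal or conservative, depending on the antiviral share. A simpler single-stage simulation, stratified by SOC only with half the subjects on no antiviral and antiviral not prognostic, gave null error of 0.0225–0.0315 under actual SOC (SE about 0.0035). At equal late-start rates of 10, 20 and 40% its power was about 96, 95 and 94%.

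**Is the Per Protocol analysis a check?** Dropping late starters gives error of 0.023–0.028 at equal rates but 0.002–0.058 at two- or three-fold differences, because exclusion also selects on a post-randomization event.

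**Cost of the as-randomized value.** With an assumed 5% of SOC entries wrong in the IWRS, error is 0.023–0.028 and power changes by at most 0.3 points.

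The logistic models were not simulated.

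**The case against.** The strongest reply is that context nearly closes the gap. Only drugs flagged as SOC count, the factor is named baseline, and both documents say the antiviral choice precedes randomization and the start comes by Day 2 noon. Misclassification needs an off-plan start and a site that flags it as SOC. All of this stands as a reason to expect few cases. It is not a programmable date rule, and the documents do not say how a site would flag a late antiviral.

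The plan also has a check: "The primary efficacy endpoint will also be analyzed on the Per Protocol set", late starters fall out of that set, and SAP 4.5 tabulates why. This stands in part, since the check is sound only when late starts are balanced by arm.

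Three stronger readings are tempting but not supported.
- **The SAP contradicts the protocol.** Protocol 11.4 specifies a "stratified Gehan-Wilcoxon test (using the randomization stratification factors, ie, type of baseline SOC and time since onset of symptoms as strata"). That names the factors, not which recorded values to use.
- **The primary test's error is inflated.** That requires two- or three-fold arm differences in late starts, with no effect on symptoms, in a double-blind trial. The documents give neither a rate nor a mechanism for this.
- **Using actual strata is itself wrong.** It is a recognised, pre-specified choice. The defect is only the missing date limit.

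**Conclusion.** The gap is real in the text: as written, an antiviral started after Day 2 noon and flagged as SOC changes the stratum used in the primary test, the confirmatory logistic models and the SOC subgroup of the full ITT-i analysis. Nothing in the documents shows that this will happen often, or unequally by arm. With equal or mildly unequal late starts, the effect on the primary test's error is within about 0.004 of nominal and hard to separate from simulation noise; at equal rates the power change is under 1.5 points either way. Larger departures rest wholly on assumed arm differences. The effect on the logistic models is unquantified. All of this depends on the assumed late-start rates, the 72 h trigger, the antiviral share and the sample-size recovery model. Severity: minor. It merits a change because the change costs so little.

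**What to change.** State in SAP 5.1.3 that the actual SOC stratum counts only SOC antivirals started within the window the plan already uses for the Per Protocol set and the OST subset (Day 2 noon), and apply the same definition to the SOC subgroup in 2.3. Add a sensitivity analysis of the primary test and the two confirmatory logistic models using SOC as randomized in the IWRS. In the simulation model above, the window makes the actual strata equal to the randomized ones.

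An acceptable alternative is to use the randomized SOC value in the main tests, with the actual value as the sensitivity analysis. Its small downside is that IWRS entry errors stay in the main analysis.

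The cost is SAP wording and one extra set of runs. Protocol 8 already has treatment periods recorded for concomitant drugs, and SAP 4.1 already tabulates both versions of the factor. The onset-time factor needs no change on this ground.

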5.2. Primary Efficacy Endpoint(s)

5.2.1. Definition

The primary efficacy analysis will be based on the ITT-i analysis set and consists of the analysis of the time to resolution of the 7 primary influenza-related symptoms.

Time to resolution of the 7 primary influenza-related symptoms (cough, sore throat, headache, nasal congestion, feeling feverish, body aches and pains, fatigue) is defined as the time in hours from initiation of study treatment to when all symptoms are considered resolved for at least 24 hours. A symptom is considered resolved, depending on pre-existence of the symptom:

- The symptom is pre-existing:
 - The symptom is considered resolved if post-baseline severity is equal or lower than the pre-existing severity
- The symptom is not pre-existing:
 - The symptom is considered resolved if its severity is scored at most mild post-baseline

A symptom is considered not pre-existing if the response to the question in the pre-existing symptoms questionnaire is 'None'. Any other non-missing response indicates that the symptom is pre-existing.

The time of resolution is the first of a successive series of 3 recordings in which all symptoms for each of the 3 assessments are considered resolved (as defined above) for all 7 primary influenza symptoms. The 3 successive recordings may have been done over 4 scheduled successive analysis timepoints, in case of 1 missing in between timepoint.

In case influenza symptoms are not resolved, data will be censored.

Censoring will be done as follows:

- 1) Last non-missing record(s) indicate resolution of influenza symptoms (but insufficient recordings to meet the time to resolution)

Censoring will be done at the first record of resolution from the last series of recordings of resolution of influenza symptoms

- 2) Last non-missing record does not indicate resolution of influenza symptoms

Censoring will be done after the last observation, which is 08:00 on the same day if the last observation was a diary entry from 00:01 until 02:00, 20:00 on the same day if the last observation was a diary entry from 02:01 until 14:00, and 08:00 the next day if the last entry was a diary entry from 14:01 until 00:00.

- 3) Additionally, in the following cases the subject will be censored using a time-to equal to the maximum time across all subjects:

- death,
- if a subject had not resolved the influenza symptoms at time of hospitalization and/or during hospitalization, and no further data on symptom resolution is available

Subjects not completing the pre-existing symptom questionnaire, or completing it after study day 1, will have values for each individual question imputed with the median response category of all subjects in the ITT-i set.

